APPENDIX E The SF-36v2 Health Survey

APPENDIX F

**Work Productivity and Activity Impairment Questionnaire:
Specific Health Problems (WPAI: SHP) Version 2.0**

Protocol MI-CP151

For Subject Completion ONLY

PID _____

Visit _ _ _

Date _ _ / _ _ / _ _ _ _

Subj Initials _ _ _

(DD/ MON/ YYYY)

**Work Productivity and Activity Impairment Questionnaire:
Specific Health Problem V2.0 (WPAI:SHP) Muscle Disease**

The following questions ask about the effect of your muscle disease on your ability to work and perform regular activities. *Please fill in the blanks or circle a number, as indicated.*

1. Are you currently employed (working for pay)? _____ NO ___ YES
If NO, check "NO" and skip to question 6.

The next questions are about the **past seven days**, not including today.

2. During the past seven days, how many hours did you miss from work because of problems associated with your muscle disease? *Include hours you missed on sick days, times you went in late, left early, etc., because of your muscle disease. Do not include time you missed to participate in this study.*

_____ HOURS

3. During the past seven days, how many hours did you miss from work because of any other reason, such as vacation, holidays, time off to participate in this study?

_____ HOURS

4. During the past seven days, how many hours did you actually work?

[figure not shown]
_____ HOURS *(If "0", skip to question 6.)*

5. During the past seven days, how much did your muscle disease affect your productivity while you were working?

Think about days you were limited in the amount or kind of work you could do, days you accomplished less than you would like, or days you could not do your work as carefully as usual. If your muscle disease affected your work only a little, choose a low number. Choose a high number if your muscle disease affected your work a great deal.

Consider only how much your muscle disease affected productivity while you were working.

[figure not shown]

CIRCLE A NUMBER

6. During the past seven days, how much did your muscle disease affect your ability to do your regular daily activities, other than work at a job?

By regular activities, we mean the usual activities you do, such as work around the house, shopping, childcare, exercising, studying, etc. Think about times you were limited in the amount or kind of activities you could do and times you accomplished less than you would like. If your muscle disease affected your activities only a little, choose a low number. Choose a high number if your muscle disease affected your activities a great deal.

Consider only how much your muscle disease affected your ability to do your regular daily activities, other than work at a job.

CIRCLE A NUMBER

[figure not shown]
**APPENDIX G Cutaneous Dermatomyositis Disease Area and Severity Index
(CDASI)**

Cutaneous Dermatomyositis Disease Area and Severity Index (CDASI)

Select the score in each anatomical location that describes the most severely affected dermatomyositis-associated skin lesion

E
x
t
e
n
t

Anatomical Location	Erythema	Scale	Excoriation	Ulceration	Poikiloderma (Dyspigmentation or Telangiectasia)	Calcinosis	Anatomical Location
	0-absent 1-pink; faint erythema 2-red 3-dark red; purple	0-absent 1-scale 2-crust; lichenification	0-absent 1-present	0-absent 1-present	0-absent 1-present	0-absent 1-present	
Scalp							Scalp
Malar Area							Malar Area
Periorbital							Periorbital
Rest of the face							Rest of the face
V-area neck (frontal)							V-area neck (frontal)
Posterior Neck							Posterior Neck
Upper Back & Shoulders							Upper Back & Shoulders
Rest of Back & Buttocks							Rest of Back & Buttocks
Abdomen							Abdomen
Lateral Upper Thigh							Lateral Upper Thigh
Rest of Leg & Feet							Rest of Leg & Feet
Arm							Arm
Mechanic's Hand							Mechanic's Hand
Dorsum of Hands (not over joints)							Dorsum of Hands (not over joints)
Gottron's – Not on Hands							Gottron's – Not on Hands

Gottron's – Hands

Examine patient's hands and double score if papules are present	Ulceration	Examine patient's hands and score if damage is present
0-absent 1-pink; faint erythema 2-red erythema 3-dark red; purple erythema		0-absent 1-scarring 2-scarring + dyspigmentation

Periungual

Periungual changes (examine)		
0-absent 1-pink; faint erythema 2-red erythema +/- cuticular dystrophy 3-telangiectasias +/- cuticular hemorrhage		

Alopecia

Recent Hair loss (within last 30 days as reported by patient)		
0-absent 1-present		

Total Activity Score

(For the activity score, please add up the scores of the left side, i.e. Erythema, Scale, Excoriation, Ulceration, Gottron's, Periungual, Alopecia)

Total Damage Score

(For the damage score, add up the scores of the right side, i.e. Poikiloderma, Calcinosis)

APPENDIX H Dermatology Life Quality Index (DLQI)

APPENDIX I Skin Photography

Locations:

- ID card and color card w/mm scale (2 each)
- Global view of the entire target area w/mm scale to measure the size of the entire lesion (2 each)

Equipment:

- Camera: Canon PowerShot S3 IS Digital 6 Mega Pixel Camera
- MM Scale Attachment Arm
- 512MB SD Cards
- SD card reader
- Color Card/Patient ID Holder
- Target Area Identification Labels
- Standardized Photographic Background

Procedures:

In these clinical photographs, for the duration of the study, the only variable allowed to change is the skin condition itself. Therefore, anything extraneous to the condition (furniture, etc.) is to be eliminated from the photographic field from the entry visit through the final visit. The necessity of good end-of-study photos should be stressed to the patients to ensure their cooperation. Lighting, framing, exposure and reproduction ratios must be held constant. In the end, the pictures should read like a time-lapse movie.

1. The supplied equipment is to be used exclusively for this study. No modification, adjustments or repairs of the camera equipment is to be undertaken without the expressed instruction of Canfield Scientific, Inc.
2. The supplied standardized background is to be used. Do not use folded or wrinkled material.
3. Close-Up Magnification: A standardized reproduction ratio of 1:3 (35MM equivalent) for the close-up view of the target area (s) is utilized. The focusing of the camera lens at 1:3 is accomplished by placing the camera in "C" (Custom) mode and confirming that the mm scale is at the bottom of the rear LCD window. The attached mm scale at the base of the camera ensures accurate focal distance.
4. Global Magnification: A standardized reproduction ratio of 1:9 (35MM equivalent) for the global view of the target area (s) is utilized. The focusing of the lens at 1:9 is accomplished by disabling the macro mode and holding the camera so that the front of the lens is approximately 37" from the surface of the target area (s).
5. If there is any doubt in your mind as to the correctness of your photographic technique, please re-shoot immediately.

6. Each photographic session includes an exposure series of:
 - a. Patient ID, which will include the following legible information in black indelible ink. (2 exposures)
 - Protocol No.
 - Date
 - Center Number
 - Visit Number
 - Patient's Initials
 - Patient's ID Number
 - Photographer's Initials
 - Color Card
 - b. Close-up of each patient's target area (s) identified with a numbered label (2 exposures)
 - c. Global view of each patient's target area (s) identified with a numbered label (2 exposures)
7. A secure, validated, compliant web server set up at [REDACTED] is used for secure transfer of study images by study sites. Images are transferred the day recorded. Remote access to all images by the Sponsor is also provided. Only approved individuals by Sponsor have access to the website.
8. [REDACTED] is to provide each study site with the necessary hardware (card reader) and instructions, as well as technical support as needed.
9. All supplied photographic equipment and photographic originals remain the property of the sponsor. Any questions or issues regarding the photographic portion of this protocol are to be forwarded to the Project Manager at [REDACTED]

APPENDIX J Guidance for Abnormal Liver Function Tests Management

This guidance is based on the October 2007 Draft Guidance of Industry Drug-Induced Liver Injury: Premarketing Clinical Evaluation.

Section IV of the FDA document deals with the clinical evaluation of and monitoring of drug-induced liver injury, and this protocol-specific guidance has adopted the draft recommendations on detection of drug-induced liver disease, confirmation of abnormal ALT/AST with regard to retesting, follow-up observation, advice on appropriate history gathering and advice on the need for obtaining additional laboratory tests and consultations as needed. We have adopted a conservative approach to holding administration of study drug based on abnormal LFTs until a full understanding of the event has been understood by the principle investigator and the medical monitor. This understanding is required so that the principle investigator, in consultation with the medical monitor, can reach a decision as to whether dosing can be continued or whether it is advisable to stop study drug permanently. The FDA document acknowledges there is no published consensus on how this decision should be made but this protocol-specific guidance requires involvement of the medical monitor at any early stage of clinically significant increases in ALT/AST to provide additional information on accumulating clinical experience of MEDI-545 as well as input from the principle investigator regarding the nature of the subject and other factors that may be relevant. This approach will provide the balance necessary to permit learning about the study drug while maximizing safety concerns to minimize the potential for functional liver impairment and damage. There are 2 separate parts to the guidance to detect clinically significant liver injury depending on whether the subject entered the study with normal or mildly elevated (up to $2 \times$ ULN) ALT/AST or on more severe abnormalities in subjects with ALT/AST $> 2 \times$ ULN at baseline.

[figure not shown]
For the purpose of this document, LFTs will be AST, ALT, total bilirubin, and alkaline phosphatase.

The decision to include subjects in this clinical trial with baseline LFT abnormalities is supported by the FDA draft guidance.

Copies of the document “Draft Guidance of Industry Drug-Induced Liver Injury: Premarketing Clinical Evaluation” can be located at <http://www.fda.gov/cder/guidance/index/index.htm>.

Guidance for abnormal Liver Function Tests during Study 151 that develop post-baseline in individuals with ALT or AST $\leq 2X$ ULN at baseline

**Occurrence post-baseline of
ALT and/or AST ≥ 5 X ULN**

Do not dose study medication

Review Clinical History:

- Hepatitis Exposure
- Infections
- For herbal, alcohol exposure
- Concomitant potentially hepatotoxic treatment
- Review all LFT's plus bilirubin, INR and alk phos

Check CK

Contact Medical Monitor (sponsor)

Hold methotrexate and other hepatotoxic medications (e.g. INH, NSAIDs, herbals, tetracyclines)

Inquire about anorexia, nausea, vomiting, RUQ pain

Consider as appropriate additional testing for Hepatitis A, B, C, CMV, EBV, ultrasounds, gi consultation

Repeat LFT immediately and weekly at the minimum

**ALT and/or
AST < 3 X ULN**

ALT and/or AST ≥ 3 X to < 5 X ULN

**ALT and/or
AST ≥ 5 X ULN**

Resume dosing study medication
Repeat LFT weekly until AST and/or ALT < 2.0 X ULN
May Resume MTX and other potentially hepato-toxic drugs as needed when AST/ALT at or near baseline

Resume dosing study medication based on clinical judgment if evidence supports isolated AST and/or ALT elevation
Repeat LFT weekly until AST or ALT are at or near baseline

Do not dose study medication

Dosing not to be resumed until discussed with Medical Monitor

Repeat LFT 2-3X weekly until AST or ALT are at or near baseline

Guidance for abnormal Liver Function Tests during Study 151 that develop post-baseline in individuals with ALT or AST > 2 X ULN at baseline

**Occurrence post- baseline of ALT and/or
AST with an increase ≥ 3 X ULN**
(**above the elevated baseline value)**

Do not dose study medication

Review Clinical History:

- Hepatitis Exposure
- Infections
- For herbal, alcohol exposure
- Concomitant potentially hepatotoxic treatment
- Review all LFT's including bilirubin and CPK as indicated. Ask about anorexia, N, V, RUQ pain

Contact Medical Monitor (sponsor)
Hold potentially hepatotoxic medications
(e.g. INH, NSAIDs, MTX, herbals, tetracyclines)

Repeat ALT, AST immediately. Bili, INR as indicated
Consider as appropriate additional testing for
Hepatitis A, B, C, CMV, EBV, liver ultrasound,
Repeat LFT weekly

**ALT and/or
AST < 3 X ULN****

Resume study medication dosing based on clinical judgment
Repeat LFT weekly until AST/ALT are at or near baseline values

May Resume MTX and other potentially hepato-toxic drugs as needed when AST/ALT at or near baseline value

**ALT and/or AST
 ≥ 3 X but ≤ 5 X ULN****

Do not dose study medication until, based on clinical judgment evidence supports an isolated AST/ALT elevation

Repeat LFT weekly and resume dosing when AST/ALT are at or near baseline values

**ALT and/or
AST > 5 X ULN****

Do not dose study medication

Required GI consultation
Repeat AST/ALT 2-3X weekly with INR, bili

Dosing not to be resumed until discussed with Medical Monitor

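### Appendix J, first chart: the low re-test box lets one enzyme below 3 x ULN permit resumed dosing while the other is still raised, which conflicts with the middle and high boxes

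*Protocol*

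**What the plan says.** Appendix J has two charts. The first is for patients whose baseline ALT or AST was at most 2 x ULN; the second is for "individuals with ALT or AST > 2 X ULN at baseline".

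In the first chart the entry trigger is a post-baseline "ALT and/or AST ≥ 5 X ULN". Drug is then withheld, the Medical Monitor is contacted, and the instruction is "Repeat LFT immediately and weekly at the minimum". The re-test leads to one of three boxes, each joining the enzymes with and/or:

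- Low, below 3 x ULN: "Resume dosing study medication", with nothing added.
- Middle, "ALT and/or AST ≥ 3 X to < 5 X ULN": resume only if clinical judgment supports an isolated elevation.
- High, at the same limit as the entry trigger: do not dose, and discuss with the Medical Monitor before resuming.

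The extra testing ends on similar wording. The low box says "Repeat LFT weekly until AST and/or ALT < 2.0 X ULN" and the high box says "Repeat LFT 2-3X weekly until AST or ALT are at or near baseline".

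The second chart works on rises above baseline and is entered at a rise of at least 3 x ULN. Its low box also uses and/or, but the action is "Resume study medication dosing based on clinical judgment".

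The introduction to Appendix J describes a conservative policy of holding drug until the investigator and the Medical Monitor understand the event. Section 3.4.4.2 refers either enzyme above 3 x ULN to Appendix J. Sections 3.4.4.2 and 4.7 end treatment after three consecutive doses missed for ALT or AST. None of these places says which box governs when the two enzymes fall in different bands.

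**The concern.** And/or is the right connective where one bad value is enough, as in a trigger or a hold. It is the wrong one for an all-clear, where both values must have recovered. A re-test with ALT 2 and AST 4 x ULN meets an unconditional resume and a judgment-only resume. A re-test with ALT 2 and AST 6 x ULN meets an unconditional resume and a hold.

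This is a dosing rule in a trial whose primary endpoints are safety and tolerability, run at about 20 sites. Two sites could act differently on the same result. The difference matters in both directions: resuming exposes a patient with a raised enzyme, while holding counts toward the three missed doses that end treatment. Discordant re-tests are plausible, because AST and ALT both belong to the trial's muscle-enzyme panel (Table 4, footnote m) and abnormal baseline values are allowed. The Protocol gives no rate for them.

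**Working it through.** There is no stated figure to reproduce. The check is to list every pair of bands and apply the boxes as worded, reading and/or as an inclusive or.

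**Inputs (Appendix J, first chart).** Bands in multiples of ULN: L is <3, M is 3 to <5, H is ≥5. Actions: L resume; M resume on judgment; H hold. Entry trigger: either enzyme ≥5.

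**Pairing of boxes and actions.** The first chart's layout is lost in the text, so its headings are paired with its actions in printed order. The second chart prints each heading directly above its action in the same low, middle, high order, and the graded actions fit no other order.

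**First chart, 3 × 3 = 9 pairs:**

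| Pair (either way round) | Cells | Boxes met as worded | Entry trigger met again? | Action if the higher enzyme governs |
|---|---|---|---|---|
| L, L | 1 | resume | no | resume |
| M, M | 1 | judgment | no | judgment |
| H, H | 1 | hold | yes | hold |
| L, M | 2 | resume and judgment | no | judgment |
| L, H | 2 | resume and hold | yes | hold |
| M, H | 2 | judgment and hold | yes | hold |

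Cells with conflicting actions: 2 + 2 + 2 = 6 of 9. Of these, 2 + 2 = 4 meet the entry trigger again, which favours a hold. The remaining 2 (L, M) do not, so nothing else in the chart settles them. These are counts of cells, not of patients.

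**Second chart.** Bands are rises of <3, 3 to 5 and >5 x ULN; the trigger is a rise ≥3. The same 6 of 9 pairs meet two boxes. Every discordant pair has at least one enzyme outside the low band, so all 6 meet the trigger again. No box there resumes without judgment.

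**After the change.** Let the higher of the two values set the branch. That value lies in exactly one band, so each of the nine pairs gets one action in either chart (last column for the first chart).

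**Stop wording.** As worded, the extra testing can end when one enzyme has recovered. While the other is still ≥5 x ULN, the entry box keeps a weekly minimum, so the most that is lost is 2-3 tests a week falling to 1. Table 4 also schedules the muscle enzymes, with AST and ALT, at every two-weekly treatment visit.

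**Who can still benefit.** Section 1.5 reports 51 patients dosed. The ceiling in Section 2.4.1 is 40 + 20 = 60, so up to 60 − 51 = 9 new patients, replacements aside, plus those still on treatment.

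**The case against.** The strongest reply is that the literal reading cannot have been meant. An isolated AST of 6 x ULN with a normal ALT would satisfy the low box at the moment it triggered the hold, and the chart would do nothing for isolated elevations, which it expressly covers. On this view and/or refers to whichever enzyme was raised. In addition, any re-test at 5 x ULN or more is itself a new trigger, the Medical Monitor has already been contacted, and the introduction asks for a conservative hold.

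Much of this stands. A reader might infer that the plan would have a patient dosed with an enzyme at 5 x ULN or more; the renewed trigger and the Medical Monitor contact make a hold far more likely. A reader might also infer that the second chart has the same unconditional resume; it does not, because its low box depends on judgment.

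Two things remain. The reading by raised enzyme is not written anywhere, and it does not settle a case where both enzymes were raised and only one has fallen below 3 x ULN. For the <3 with 3 to <5 pairs there is no renewed trigger. The explicit bar on resuming before Medical Monitor discussion stands only in the high box, so that protection depends on which box the site picks.

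**Conclusion.** The point holds as a drafting error in a safety rule, with limited harm. Six of nine band pairs in the first chart carry two different instructions. Four are likely to be resolved toward a hold by the entry trigger; the two that pair <3 with 3 to <5 x ULN are left open between unconditional and judgment-based resumption. It is worth correcting because the rule should have one meaning and the correction is cheap.

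The conclusion assumes the box order described above and an inclusive reading of and/or. No frequency can be attached to it.

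Two further inferences are not supported. A reader might conclude that the stop wording leaves a raised enzyme unmonitored; the weekly minimum and the two-weekly panel prevent that, so it is only a matching edit. A reader might also note that both chart titles fit a patient with one enzyme above and one at or below 2 x ULN at baseline, and infer that each enzyme should follow its own chart's limits. Nothing in the Protocol supports such a scheme, the introduction points toward the second chart for that patient, and the choice is clinical.

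**What to change.** In the first chart, word the low box as *both ALT and AST < 3 x ULN*, the high box as *either ALT or AST ≥ 5 x ULN*, and the middle box as *all other pairs*. In the second chart, make the matching change: both rises < 3 x ULN for the low box, either rise > 5 x ULN for the high box, all other pairs in the middle. The higher enzyme then sets the branch. As a minor companion edit, end the extra repeat testing only when both enzymes meet the stop limit.

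This is one appendix page, in the next amendment or a clarification memo. The downside is a few more held doses or repeat tests in patients with discordant enzymes, some of which could count toward the three consecutive missed doses that end treatment under Section 4.7.

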APPENDIX K Changes to the Protocol

Summary of Changes from Version 1.0 to Version 2.0 of the Study Protocol

Version 1.0 of the protocol (dated [REDACTED]) was amended to Version 2.0 (dated [REDACTED]) to provide more information about genetic testing; to include pregnancy testing before each dose of MEDI-545 and every 12 weeks thereafter; to exclude patients with a history of active tuberculosis; to clarify that Quantiferon-TB Gold assay for the diagnosis of latent tuberculous infection will be done at selected sites; to clarify that IVIG may be given in the study; to clarify other events requiring immediate reporting, and to correct typographical errors. The changes made to Version 1.0 of the protocol to create Version 2.0 are summarized below.

Some of these changes occur in multiple places in the protocol but are presented in the most relevant sections. These changes, if applicable, also apply to the Study Abstract. Text that has been added is shown bolded and underlined; text that has been deleted is shown strike-through.

1. Section 2.4.2 (also referenced in Study Abstract under Patient Evaluation and Follow-up)

Changed to read:

Screening evaluations include the following: medical history; physical examination; body weight; chest x-ray; ECG; tuberculosis skin test; blood tests for hepatitis A, B, C, human immunodeficiency virus (HIV)-1 and HIV-2; **Quantiferon®-TB Gold assay for tuberculosis**; serum β human chorionic gonadotropin (β HCG) for women (unless surgically sterile or 2 years after menopause); vital signs; serum chemistry (including Na, K, Cl, bicarbonate, blood urea nitrogen [BUN], creatinine, bilirubin, alkaline phosphatase, and random glucose); complete blood count (CBC) with differential and platelets, serum levels of muscle enzyme (including CK, aldolase, LDH, ALT, and AST); urinalysis; manual muscle testing (MMT), extramuscular activity assessment based on Myositis Disease Activity Assessment Tool (MDAAT), pulmonary function tests, physician global activity assessment; and clinical Health Assessment Questionnaire (CLINHAQ).

Safety assessments include AE and SAE evaluation, physical examination, vital signs, serum chemistry panel, CBC with differential and platelets, urinalysis, and viral surveillance testing via oropharyngeal swabs for herpes simplex virus (HSV)-1 and HSV-2; vaginal swabs (women) for HSV-1, HSV-2, and human papillomavirus (HPV); **Quantiferon®-TB Gold assay for tuberculosis (at selected sites)**; and blood tests for Epstein Barr virus (EBV) and cytomegalovirus (CMV).

Reason for Change: The Quantiferon®-TB Gold assay for tuberculosis will be performed at selected sites that have the facilities to perform this test. This assay has been moved from screening to Study Day 0.

2. Section 3.1.1

Changed to read:

5. All patients including those with DM must meet at least two of the following criteria:
 - a. Strength in MMT greater \geq 80/150 but \leq 125/150 using the MMT-8 muscle group testing (see Appendix A);

- b. Patient Global Activity Assessment by visual analog scale (VAS) ≥ 2.0 cm on a 10 cm scale, **which is included as part of CLINHAQ (see Appendix B);**
- c. Physician Global Activity Assessment by VAS ≥ 2.0 cm on a 10 cm scale, **which is included as part of MDAAT (see Appendix C);**
- d. CLINHAQ (see Appendix B) disability index ≥ 0.25 ;
- e. Global extramuscular activity assessment ≥ 1.0 cm on a 10-cm VAS scale (this measure is the physician's composite evaluation and is based on assessments of activity scores on the constitutional, cutaneous, skeletal, gastrointestinal, pulmonary and cardiovascular scales of the MDAAT [Appendix C]);

Reason for Change: Clarification of text.

3. Section 3.1.2

Changed to read:

19. History of active ~~or latent~~ tuberculous infection ~~without completion of an appropriate course of treatment and with evidence of active infection on chest x ray;~~

Added:

20. **History of latent tuberculous infection without completion of an appropriate course of treatment;**

Reason for Change: Exclusion of patients with a history of active tuberculosis infection.

4. Section 3.2

Changed to read:

- MedImmune calls and informs the **IVRS investigator** of patient eligibility to participate based on the expression of mRNA for type I IFN-inducible genes;

Reason for Change: Clarification of text.

5. Section 3.4.2

Added cross-reference to Table 1 for clarification of text.

6. Section 3.4.5

Changed to read:

All concomitant medications used by the patient from screening through Study Day 350 will be recorded on the case report form. **The concomitant administration of intravenous immunoglobulin (IVIG) is allowed.**

Patients may not receive the following from screening through Study Day 350:

1. Investigational agents (eg, rituximab for myositis);
2. Any live attenuated virus vaccine;
3. Hydroxychloroquine > 600 mg/day, mycophenolate mofetil > 3 g/day, methotrexate > 25 mg/week, leflunomide > 20 mg/day, azathioprine > 3 mg/kg/day; or
4. Any dose of cyclophosphamide, cyclosporine, or thalidomide.

~~The sponsor must be notified if any patient receives prohibited concomitant medications.~~

Corticosteroid doses may not exceed 35 mg/day of prednisone or an equivalent dose of another corticosteroid. Corticosteroid doses must remain constant from 14 days before Study Day 0 through Study Day 196. Thereafter, corticosteroid doses may be increased, tapered, and discontinued as considered appropriate by the investigator.

Reason for Change: Clarification of allowed concomitant medications.

7. Section 3.5

Deleted

~~Patients who withdraw consent during the study should~~

Reason for Change: Correction of typographical error.

8. Section 3.5 (Table 2 and Table 3) and Description of Visits

Added ECGs at Study Days 42 and 140 for additional safety information.

Added urine pregnancy testing (urine β HCG) on Study Days 14, 28, 42, 56, 70, 84, 98, 112, 126, 140, 154, 168, 182, 266, and 350.

Reason for Change: Increased frequency of pregnancy testing as an additional assessment of safety.

Moved Quantiferon-TB Gold assay from screening to Study Day 0.

Changed Footnote “g” and corresponding visits for consistency of vital signs monitoring as follows:

- g. Vital signs include heart rate, blood pressure, respiratory rate and temperature. Blood pressure should be obtained with the patient in the position to be used for drug administration. **~~On Study Days 0 and 98,~~** Vital signs will be monitored before **and immediately after** study drug administration and every 30 minutes after study drug administration **~~for at least 2 hours or until stable and at discharge. On all other treatment visits, vital signs will be monitored before study drug administration and at least 30 minutes after study drug administration or until stable.~~**

Added Footnote “q” to state that Quantiferon-TB Gold assay will be done at selected sites.

Reason for Change: The Quantiferon®-TB Gold assay for tuberculosis will be performed at selected sites that have the facilities to perform this test.

Added Footnote “r” stating that chest x-rays taken within 6 months of screening will be considered suitable for screening and need not be repeated.

Reason for Change: To allow use of prior chest x-rays for screening purposes.

Added Footnotes “s” and “t” to clarify that Physical Global Activity Assessment is included as part of MDAAT and Patient Global Activity Assessment is included as part of CLINHAQ.

Reason for Change: Clarification of text.

9. Section 3.5 (Description of Visits)

Changed to read (Screening Visit):

- Serum β HCG (**for women who are sexually active and are not surgically sterile or at least 2 years postmenopausal; this test must be negative for study participation**)

Changed to read (Study Day 0, 14, 28, 42, 56, 70, 84, 98, 112, 126, 140, 154, 168, 182, 266, and 350 Visits):

6. Urinalysis, **includes collection of urine for β HCG (for women who are sexually active and are not surgically sterile or at least 2 years postmenopausal; this test must be negative for study participation)**

Reason for Change: Clarification of text.

10. Section 3.6.1

Changed to read:

Urine pregnancy tests will be performed in female subjects who are not postmenopausal or surgically sterile at the time of screening on **Study Day 0, prior to study drug administration on Study Days 14, 28, 42, 56, 70, 84, 98, 112, 126, 140, 154, 168, and 182, and on Study Days 266 and 350** using a licensed test. New clinically significant abnormal laboratory results, which in the opinion of the investigator are related to safety, should be repeated as soon as possible (preferably within 24–48 hours).

Reason for Change: Clarification of text.

11. Section 3.6.3

Changed to read:

At screening, patients will receive tuberculin skin test. Those who are known to have positive tuberculin skin test should not receive the skin test and should be confirmed by chest x-ray that they have had no evidence of active tuberculosis. **Reading of the tuberculin skin test should be performed 48 to 72 hours after administration by a trained health professional. The 10 mm cut point will be used to determine tuberculin skin test positivity.** Those who have ~~had a history of active or~~ latent tuberculosis ~~in the past~~ must have completed an appropriate course of anti-tuberculosis treatment. During the study, **at selected sites**, patients will receive Quantiferon-TB Gold tests as described in CDC guidelines to monitor for tuberculosis (Mazurek, 2005).

Reason for Change: Added information describing positive tuberculin skin test, and clarified language regarding latent tuberculosis.

12. Section 3.6.5.2

Changed to read:

Physician Global Activity Assessment is included as part of MDAAT, and Patient Global Activity Assessment is included as a part of CLINHAQ.

Changed Table 4 to be consistent with the text.

Reason for Change: Clarification of text.

13. Section 3.6.5.4

Changed to read:

Lack of evidence of active myositis is defined as assessed by global and extramuscular assessments ~~using IMACS forms~~, stable muscle strength and function (defined as equivalent to < 15% change in the semiquantitative scoring of the measures of these domains over at least a 6-month period), and normal muscle enzyme levels.

Reason for Change: Clarification of text.

14. Section 3.6.5.8

Corrected publication year (Ware, 1992).

15. Section 3.6.6

Changed to read:

Correlative studies include collection of serum for assessment of autoantibodies and proteomics, collection of serum for IFN- α assays and other exploratory research, ~~whole blood for gene expression analyses~~, peripheral blood for flow cytometry, and muscle and skin biopsies, ~~and whole blood for DNA analysis~~. The follow-up muscle biopsy should be done on the contralateral muscle, and the follow-up skin biopsy should be done in close proximity to the first biopsy.

Other correlative studies include collection of whole blood for type I interferon inducible gene expression and analysis of DNA. Collection of blood for DNA analysis is voluntary, and patients must sign a separate informed consent form (Informed Consent Form for Collection of Blood Samples for DNA Analysis) in order for this test to be done. Patients who do not wish to have the DNA test done will still be eligible for the study.

Reason for Change: To provide more information on the analysis of whole blood for type I interferon inducible gene expression and analysis of DNA.

16. Section 3.6.6.3

Changed to read:

Open Muscle biopsies will be performed at visits indicated in Table 2. **The initial muscle biopsy will be performed on an involved muscle within 7 days prior to Study Day 0. Involved muscle is defined as having a muscle strength of 4 to 4-/5 as assessed by MMT. The repeated muscle biopsy will be performed on a muscle that was noted to be involved on Study Day 0. If involved on Study Day 0, the contralateral muscle is the preferred site of the repeated biopsy.** Muscle biopsy samples collected during the trial will undergo histopathological grading and IHC analysis of cellular infiltrates, including dendritic cell subtypes, B cells, and T cells. Additionally, gene expression will be analyzed, and changes in IFN-inducible protein levels within muscle specimens will be assessed by IHC methods.

Reason for Change: Specified the use of involved muscle for the muscle biopsies.

17. Section 3.6.6.6

Changed to read:

The pharmacodynamics of MEDI-545 will be studied through analyses of its effects on type I IFN-inducible gene expression in whole blood, muscle, and skin. The levels of mRNA for type I IFN-inducible genes will be measured using genomic tests. PCR assay on selected panel of genes may be used to confirm the results. **The analysis in whole blood is performed using Affymetrix whole genome expression array and taqMan-based assay on selected panel of genes. In muscle and skin, immunohistochemical methods will be used to stain for a pre-selected panel of genes that will allow further assessment of the pathogenesis of inflammatory muscle disease. Subsequent studies will be dependent upon the results obtained from our initial analyses.**

Reason for Change: To provide more information on the analysis of whole blood for type I interferon inducible gene expression.

18. Section 3.6.6.7

Changed to read:

To investigate characteristics associated with patients' clinical response and safety, one blood sample (8.5 mL) will be collected on Study Day 0 and frozen at -80°C for DNA sample preparation. The sample will be frozen and stored until used in exploratory analyses. The specific tests include analyses for DNA single nucleotide polymorphisms (SNPs) and microsatellite or short tandem repeats to further evaluate particular genes involved in the signaling pathway relevant to type I interferons.

The collection of blood for DNA analysis is optional. The completion of a separate informed consent form (Informed Consent Form for DNA Analysis) is requested but not required for participation in the trial. Patients who do not wish to have the DNA test done will still be eligible for the study. **Patients who elect to have the DNA test done may, at any time, request that the blood collected for DNA analysis be destroyed.**

All specimen and patient identifiers must be removed from the DNA blood samples such that under no circumstances can the DNA blood samples be linked back to a specific patient. In most cases, this will require that DNA blood samples have current labeling removed and the tubes relabeled. Special labeling capable of adhering to frozen tubes must be used. If it is not possible to remove the original labeling, then it must be determined whether the DNA blood samples can go through a freeze thaw and be re-aliquoted in order to maintain confidentiality. All re-labeled DNA blood samples must be cross referenced to the original demographics in a secure database to ensure that only appropriate laboratory personnel have access to these data. A special release must be obtained prior to use of specified DNA blood samples.

Reason for Change: To provide more information and clarification of text on the analysis of whole blood for analysis of DNA.

19. Section 4.4

Changed to read:

An **SAE** is considered “product-related” for the purposes of regulatory reporting if the Investigator, the Medical Monitor, or the Product Safety Physician assesses the SAE as possibly, probably, or definitely related to study drug. This is not a conclusive determination of causal association between the product and the event. Whenever the Investigator’s assessment is unknown or unclear, the **SAE** is treated as product-related for the purposes of reporting to regulatory authorities. An **SAE** may be deemed to be not related to the product for purposes of regulatory reporting only if the Investigator, Medical Monitor, and Product Safety Physician, if applicable, agree that the **SAE** is not product-related.

Reason for Change: Clarification of text.

20. Section 4.5

Changed to read:

In addition to SAEs, the following events must be reported *within 24 hours* by fax to MedImmune Product Safety:

1. Any withdrawal of consent during the study
2. Pregnancy or intent to become pregnant*
3. Severe hypersensitivity reaction to the study drug, Grade 3 or higher
4. Severe viral infection, Grade 3 or higher
- 5. Any event which, in the opinion of the investigator or the Medical Monitor, contraindicates further dosing such as illnesses or complications.**

*Patients who become pregnant during the study period must not receive additional doses of study product but will be followed on study. A pregnancy should be followed for outcome, any premature terminations reported, and the health status of the mother and child including date of delivery and the child’s gender and weight should be reported to MedImmune Product Safety after delivery.

Reason for Change: Clarification of text.

21. Section 4.8

Deleted:

~~**Patients who are in lower dose cohorts may continue to be dosed:**~~

Reason for Change: Clarification of text.

22. Section 11

Deleted references not cited in protocol, and **corrected** and **added** references that were noted in the text but not in the reference section.

Reason for Change: Clarification of text.

23. Appendix C

Replaced Appendix C with a modified version of the MDAAT stipulating that assessments of muscle disease involvement must be made in the absence of muscle enzyme laboratory test results. This change was made to prevent unblinding of the study.

24. Appendix H

Replaced Appendix H with a validated version of the CDASI.

Summary of Changes from Version 2.0 to Version 3.0 of the Study Protocol

